### 2. STUDY HYPOTHESES / OBJECTIVES

## 2.1 HYPOTHESIS

The primary clinical hypothesis is that inhibition of the IL-15 pathway with AMG 714 will deplete autoreactive resident memory T cells in the skin and modulate pro-inflammatory mediators, resulting in durable repigmentation of skin affected by vitiligo.

#### 2.2 PRIMARY OBJECTIVE

The primary objective is to determine the efficacy of IL-15 inhibition with AMG 714 at inducing facial skin repigmentation in vitiligo.

### 2.3 SECONDARY OBJECTIVES

The secondary objectives are to:

- 1. Evaluate the safety and tolerability of AMG 714 in vitiligo.
- 2. Determine the efficacy of IL-15 inhibition with AMG 714 at inducing total body skin repigmentation in vitiligo.
- 3. Assess the durability of the skin repigmentation achieved by AMG 714 in vitiligo.
- 4. Evaluate the efficacy of AMG 714 followed by narrow band UVB (nbUVB) phototherapy.

## 2.4 EXPLORATORY OBJECTIVES

Exploratory mechanistic objectives are described in Section 9.

#### 3. STUDY DESIGN

### 3.1 DESCRIPTION OF THE STUDY DESIGN

This clinical trial is a phase 2a, double blind, placebo-controlled, multi-center, proof of concept trial of AMG 714 for the treatment of vitiligo. Fifty-seven participants ages 18-75 years old with vitiligo will be randomized 2:1 to receive AMG 714 300 mg or placebo subcutaneously every 2 weeks for 6 doses beginning at Week 0 with the last dose at Week 10. Participants will be stratified based on vitiligo activity, as defined in Section 3.4. The primary endpoint will be assessed at Week 24. Participants with < 25% improvement in the T-VASI score at Week 24 compared to Week 0 will receive nbUVB phototherapy. Participants will be followed for an additional 24 weeks after assessment of the primary endpoint to evaluate change in the F-VASI and T-VASI scores through Week 48 with or without the addition of nbUVB, and to continue to collect safety information. The target enrollment duration is 14 months. Figure 1 provides a schematic of the study design for this trial and Figure 2 provides an overview of individual study participation.

Figure 1. Study Design

[figure not shown]
[figure not shown]

Figure 2. Individual Study Participation

#### 3.2 PRIMARY ENDPOINT

Proportion of participants achieving  $\geq$  35% improvement in F-VASI (F-VASI35) at Week 24 compared to Week 0.

#### 3.3 SECONDARY ENDPOINTS

## 3.3.1 Secondary Efficacy Endpoints

- 1. Proportion of participants with F-VASI35 at Weeks 12, 36, and 48.
- 2. Proportion of participants with F-VASI25, F-VASI50, F-VASI75, and F-VASI90 at Weeks 12, 24, 36, and 48.
- 3. Proportion of participants with T-VASI25, T-VASI35, T-VASI50, T-VASI75, and T-VASI90 at Weeks 12, 24, 36 and 48.
- 4. Change in each of the following at Weeks 12, 24, 36, and 48 compared to Week 0:
  - a. F-VASI
  - b. T-VASI
  - c. Vitiligo Extent Score (VES)36
  - d. Vitiligo Quality of Life instrument (VitiQoL)
  - e. Vitiligo Noticeability Scale (VNS)38
  - f. Static Investigator Global Assessment (sIGA)
- 5. Percent change in each of the following at Weeks 12, 24, 36, and 48 compared to Week 0:
  - a. F-VASI
  - b. T-VASI

### 3.3.2 Secondary Safety Endpoints

- 1. Grade 2 or higher adverse events (AEs).
- 2. Grade 3 or higher infectious AEs.

#### 3.4 **DEFINITIONS**

#### 3.4.1 F-VASI35

F-VASI35 is defined as  $\geq$  35% improvement in the F-VASI score compared to Week 0, according to the following formula:

F-VASI < 0.65 (F-VASI at Week 0)

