## PROTOCOL SYNOPSIS

Title	Evaluation of AMG 714 for Vitiligo: A Phase 2a Randomized Double Blind Placebo Controlled Trial	
Short Title	Evaluation of AMG 714 for Vitiligo	
Clinical Phase	Phase 2a	
Number of Sites	5-10 sites	
IND Sponsor / Number	DAIT, NIAID / IND 146561	
Study Objectives	The primary objective is to determine the efficacy of IL-15 inhibition with AMG 714 at inducing facial repigmentation in vitiligo.  The secondary objectives are to:  1. Evaluate the safety and tolerability of AMG 714 in vitiligo. 2. Determine the efficacy of IL-15 inhibition with AMG 714 at inducing total body skin repigmentation in vitiligo. 3. Assess the durability of the skin repigmentation achieved by AMG 714 in vitiligo. 4. Evaluate the efficacy of AMG 714 followed by narrow band UVB (nbUVB) phototherapy.	
Study Design	This clinical trial is a phase 2a, double blind, placebo-controlled, multi-center, proof of concept trial of AMG 714 for the treatment of vitiligo. Fifty-seven participants ages 18-75 years old with vitiligo will be randomized 2:1 to receive AMG 714 300 mg or placebo subcutaneously (SQ) every 2 weeks for 6 doses beginning at Week 0 with the last dose at Week 10. Participants will be stratified based on vitiligo activity, as defined in Section 3.6. The primary endpoint will be assessed at Week 24. Participants with < 25% improvement in the T-VASI score at Week 24 compared to Week 0 will receive nbUVB phototherapy. Participants will be followed for an additional 24 weeks after assessment of the primary endpoint to evaluate change in the F-VASI and T-VASI scores through Week 48 with or without the addition of nbUVB, and to continue to collect safety information.	
Primary Endpoint	Proportion of participants achieving≥35% improvement in F-VASI (F-VASI35) at Week 24 compared to Week 0.	
Secondary Endpoints	
 
Proportion of participants with F-VASI35 at Weeks 12, 36, and 48.
 
Proportion of participants with F-VASI25, F-VASI50, F-VASI75, and F-VASI90 at Weeks 12, 24, 36, and 48.
 
Proportion of participants with T-VASI25, T-VASI35, T-VASI50, T-VASI75, and T-VASI90 at Weeks 12, 24, 36 and 48.
 
	

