	
 
4. Change in each of the following at Weeks 12, 24, 36, and 48 compared to Week 0: 
 
a. F-VASI
 
b. T-VASI
 
c. Vitiligo Extent Score (VES)
 
d. Vitiligo Quality of Life instrument (VitiQoL)
 
e. Vitiligo Noticeability Scale (VNS)
 
f. Static Investigator Global Assessment (sIGA)
 
 
 
5. Percent change in each of the following at Weeks 12, 24, 36, and 48 compared to Week 0: 
 
a. F-VASI
 
b. T-VASI
 
 
 
Safety endpoints: 
 
1. Grade 2 or higher adverse events (AEs).
 
2. Grade 3 or higher infectious AEs.
 
 
 
	
Accrual Objective	57	
Study Duration	The target enrollment duration is 14 months. Participants will be followed for 48 weeks.	
Treatment Description	AMG 714 300 mg or placebo injected subcutaneously every 2 weeks for 6 doses.	
Inclusion Criteria	
 
Adults 18-75 years of age.
 
Clinical diagnosis of active or stable vitiligo made by a dermatologist, as defined in Section 3.4.2.
 
F-VASI ≥ 0.25 (Appendix 2).
 
T-VASI ≥ 3 (Appendix 2).
 
Willingness to:         
 
undergo nbUVB phototherapy, as outlined in Section 7.3.
 
Stop all other treatments for vitiligo from screening through the final follow up visit as outlined in Section 7.2.
 
 
 
	
Exclusion Criteria	
 
Inability or unwillingness of a participant to give written informed consent or comply with the study protocol.
 
Segmental vitiligo.
 
Contraindication to nbUVB phototherapy.
 
More than 33% leukotrichia on the face or on the total body.
 
Use of biologic immunosuppressive or immunomodulatory agents, or investigational therapy or procedure within 12 weeks or 5 half-lives prior to Visit 0 (whichever is longer), except agents authorized for prevention and treatment of SARS-CoV-2 infection according to FDA Emergency Use Authorization (EUA).
 
	

- 6. Use of laser or light-based treatment (phototherapy) including tanning beds within 8 weeks prior to Visit 0.
- 7. Use of non-biologic systemic or topical immunosuppressive or immunomodulatory agents within 4 weeks prior to Visit 0.
- 8. History of melanocyte-keratinocyte transplantation procedure (MKTP) or other surgical treatment for vitiligo.
- 9. Current or pastuse of the depigmenting agents monobenzyl ether of hydroquinone, including Benoquin® (Monobenzone).

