# 13.4.2 Primary Analysis of Primary Endpoint

The primary endpoint is the proportion of participants achieving an F-VASI35 response at Week 24.

The primary analysis of the primary endpoint will be performed on the mITT sample and is designed to test the following hypotheses:

- Null hypothesis: The proportion achieving an F-VASI35 at Week 24 does not differ between the AMG 714 and placebo groups
- Alternate hypothesis: The proportion achieving an F-VASI35 at Week 24 differs between the AMG 714 and placebo groups.

The proportion of F-VASI35 responders will be estimated for each treatment group. Groups will be compared using two-sided Fisher's Exact test evaluated using a Type 1 error rate of  $\alpha$ =0.05.

**Missing Data.** For a participant who is missing the baseline F-VASI, the screening F-VASI will be used. Participants for whom the Week 24 F-VASI cannot be evaluated will be deemed non-responders.

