#### **APPENDIX 2. VASI**

#### Vitiligo Area Scoring Index (VASI)

The vitiligo area scoring index (VASI) is a quantitative clinical tool to assess the area affected by vitiligo. The body is divided into 6 separate regions:

- Head and neck (includes face)
- Upper extremities (excluding hands). The axillae are considered part of the upper extremities.
- Hands
- Torso (excluding axillae). The genitalia are not included in the VASI assessment.
- Lower extremities (excluding feet). The buttocks and inguinal area are considered part of the lower extremities.
- Feet

For each body region, the VASI is determined by the product of the area of vitiligo in hand units and the extent of depigmented skin within each hand unit-measured patch (estimated to the nearest of the following percentages: 0%, 10%, 25%, 50%, 75%, 90% or 100%).

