#### Calculation of the F-VASI

The F-VASI will be calculated separately. The F-VASI will be calculated in the same fashion as the T-VASI, except that the evaluable area is limited to the face only (see above). The %BSA will be measured to the tenth decimal (0.1%). The evaluable area is all of the following:

1. From the top of the forehead at the hairline down to the jawline, and from the right to the left tragus anteriorly, excluding mucosal lips. For participants who have a receding hairline, the original hairline should be used as the border for the face.

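### Section 3.4.1 defines F-VASI35 as at least 35% improvement, but its formula reads as a strict inequality, so an exact 35% improvement counts as non-response

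*Combined protocol and SAP*

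**What the plan says.** The Synopsis gives the primary endpoint as "Proportion of participants achieving≥35% improvement in F-VASI (F-VASI35) at Week 24 compared to Week 0". Section 3.2 repeats it, with the at-least sign before "35% improvement in F-VASI (F-VASI35) at Week 24 compared to Week 0". Section 3.4.1 states it a third time, again inclusively, as "35% improvement in the F-VASI score compared to Week 0, according to the following formula", and the formula that follows is "F-VASI < 0.65 (F-VASI at Week 0".

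Section 13.4.2 tests F-VASI35 response without restating the rule: "Groups will be compared using two-sided Fisher's Exact test evaluated using a Type 1 error rate of" 0.05. It adds no rule for ties or rounding. The plan gives no formula for the other F-VASI and T-VASI cut-offs.

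Appendix 2 makes F-VASI a product of two coarse quantities. For area, "The %BSA will be measured to the tenth decimal (0.1"%). Depigmentation is "estimated to the nearest of the following percentages: 0%, 10%, 25%, 50%, 75%, 90% or 100"%. The face form has one row and a maximum area of 3.5%. Eligibility requires "F-VASI ≥ 0.25 (Appendix 2").

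**The concern.** The definition and the formula are meant to be the same rule, and Section 3.4.1 presents the second as the way to apply the first. They agree everywhere except at equality, where they give opposite answers. F-VASI takes a limited set of values, so equality can occur.

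The rule fixes responder status for the primary test in a trial of 57 participants. If the formula were programmed literally, a participant who meets the stated endpoint would be counted as a failure. If the conflict surfaced only once data were in hand, someone would have to choose between the two rules after the fact.

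**Working it through.** **1. The plan's own figure.** Section 13.7 gives 88% power for 45% v 5% with 57 participants at 2:1, that is 38 v 19. The arcsine approximation to Fisher's exact test with continuity correction reproduces it:

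- adjusted rates: 0.05 + 1/(2×19) = 0.0763 and 0.45 − 1/(2×38) = 0.4368
- z = 2 × (arcsin√0.4368 − arcsin√0.0763) × √(38×19/57) − 1.96 = 2 × (0.7221 − 0.2799) × 3.559 − 1.96 = 1.19
- power = Φ(1.19) = 0.88

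The same method gives 81% at 7.5% placebo response and 80% at N = 48, as stated. (Direct enumeration of the two-sided Fisher test gives 92.7% for the first case, so 88% is conservative.) The calculation takes the response rates as given. An inclusive formula is the endpoint already stated in words, so correcting the sign leaves the 88% unchanged.

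**2. Algebra.** Improvement = (V0 − V24)/V0. Improvement ≥ 0.35 is equivalent to V24 ≤ 0.65 × V0. The formula V24 < 0.65 × V0 is equivalent to improvement > 0.35. The two differ only when V24 = 0.65 × V0. With V0 = 2.0, 0.65 × 2.0 = 1.3; at V24 = 1.3 the words give a responder, and 1.3 < 1.3 is false.

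**3. Can ties occur?** Take areas 0.0 to 3.5 in steps of 0.1, the seven depigmentation levels, and baseline F-VASI ≥ 0.25, in exact fractions. There are 166 eligible baseline states. Eight can reach exactly 0.65 of baseline with neither component worsening, each through one follow-up state:

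| Baseline area × depigmentation | Week 24 area × depigmentation | F-VASI |
|---|---|---|
| 2.0 × 1.00 | 1.3 × 1.00 | 2.0 to 1.3 |
| 2.0 × 0.90 | 1.3 × 0.90 | 1.8 to 1.17 |
| 2.0 × 0.75 | 1.3 × 0.75 | 1.5 to 0.975 |
| 2.0 × 0.50 | 1.3 × 0.50 | 1.0 to 0.65 |
| 2.0 × 0.25 | 1.3 × 0.25 | 0.5 to 0.325 |
| 1.5 × 1.00 | 1.3 × 0.75 | 1.5 to 0.975 |
| 1.8 × 1.00 | 1.3 × 0.90 | 1.8 to 1.17 |
| 3.0 × 1.00 | 2.6 × 0.75 | 3.0 to 1.95 |

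If one component may worsen while the score falls, the count is 16 of 166. By distinct baseline score it is 7 of 111 on the single row, and 33 of 597 if two patches are summed. These count where a tie is possible. They do not say how often one happens.

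**4. What one tie could do.** The two-sided Fisher p-value sums the hypergeometric probabilities C(38,x)·C(19,m−x)/C(57,m) over all tables with m responders that are no more likely than the one observed. With 1/19 on placebo:

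- 11/38 on AMG 714 (m = 12): p = 0.045
- 10/38 on AMG 714 (m = 11): p = 0.079

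Now suppose one AMG 714 responder is lost to a tie. The probability that the result is significant with that responder and not significant without is the sum of binomial probabilities over tables with p(x, y) ≤ 0.05 and p(x − 1, y) > 0.05:

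- 45% v 5% (the planned rates): 3.4%
- 30% v 5% (an assumed weaker effect): 9.2%

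A tie in the placebo arm would move the p-value the other way.

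**5. Allowing for how rare ties are.** The documents give no tie rate. As an assumption, take 0.05% to 0.5% per participant. The chance of at least one tie among 38 is then 1 − 0.9995^38 = 1.9% to 1 − 0.995^38 = 17%. Multiplied by the figures in step 4, the chance of a changed conclusion is about 0.019 × 0.034 = 0.06% to 0.17 × 0.092 = 1.6%.

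**The case against.** The strongest objection is that the whole point rests on one character. In the text as read from the PDF, the white-cell exclusion carries a less-than-or-equal sign in the Synopsis and a less-than sign in Section 4.3, so these two signs cannot be relied on without the original. The at-least sign survives in the same section, but that does not vouch for the formula's sign. This objection stands, and it makes checking the original the first step.

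The intent is also clear. The inclusive threshold is stated three times, and the phototherapy rule is framed the same way: Section 7.3 uses improvement of at least 25%, and Section 3.1 uses its exact complement. A careful programmer would probably follow the words. That lowers the risk but does not remove the conflict, because Section 3.4.1 offers the formula as the way to apply the definition.

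A reader might go further and infer three things that the documents do not support:

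- *That the trial runs a 3% to 9% risk of losing its result.* Those figures assume that a tie has already occurred in an AMG 714 participant. The 11 v 10 example also sits on the significance boundary, whereas the planned rate implies about 0.45 × 38 = 17 responders.
- *That the other VASI cut-offs carry the same error.* No formula is given for them, so there is no sign to correct.
- *That floating-point arithmetic already threatens the endpoint.* Computed as percent change ≥ 0.35, 5 of the 8 ties are misclassified, but the plan does not specify that expression. The form V24 ≤ 0.65 × V0 classifies all 8 correctly.

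**Conclusion.** The inconsistency is real in the text as it stands: the operative formula for the primary endpoint contradicts the endpoint's definition at exactly 35% improvement. It is worth correcting because the rule decides the primary test and the correction is almost free.

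Its size is minor. Only exact ties are affected, and they should be rare; stated power does not change. The count of tie-capable states assumes the one-row face form, and any unconditional risk depends on a tie rate that has to be assumed. If the original PDF shows a less-than-or-equal sign, the contradiction disappears and only a short note on how to compute ties is left.

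**What to change.** 1. Check the sign in Section 3.4.1 against the original PDF.
2. If it is strict there, change the formula to F-VASI at Week 24 ≤ 0.65 × F-VASI at Week 0, so that it matches the Synopsis and Section 3.2.
3. Use the same inclusive convention when programming the 25, 50, 75 and 90% F-VASI cut-offs and all T-VASI cut-offs. This matters most for T-VASI25. If a strict form were carried over, a participant with exactly 25% improvement would be coded a non-responder yet would not meet the phototherapy criterion in Sections 3.1 and 7.3, and so would fall outside both post-Week 24 subsets in Section 13.4.4.
4. State in the programming specification that the comparison is made on exact or suitably rounded values in the product form above.

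The cost is one symbol and one programming note. Sample size, visits and the planned test are unaffected. The correction should be made before unblinding.

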#### 3.4.2 Vitiligo Activity

- 1. Active vitiligo: New or expanding vitiligo lesions with or without the presence of confetti, trichrome, or inflammatory vitiligo lesion patterns, Koebner phenomenon, or other clinical signs of active vitiligo in the past 3 months.
- 2. Stable vitiligo: No new depigmented lesions, and no confetti, trichrome, or inflammatory vitiligo lesion patterns, Koebner phenomenon, or other clinical signs of active vitiligo in the past 3 months.

## 3.5 STRATIFICATION, RANDOMIZATION, AND BLINDING/MASKING

Participants who sign the informed consent form and meet the eligibility criteria will be randomly assigned 2:1 in favor of treatment with AMG 714 versus treatment with placebo. Random assignment will be stratified by active versus stable vitiligo, as defined in Section 3.4.2.

Randomization will be accomplished through a password-protected, web-based, randomization system.

Randomization will occur at least one day prior to Visit 0.

## 3.5.1 Blinding

Blinding will be maintained for all study participants and trial personnel throughout the study, except for the study site Pharmacist of Record (PoR). As an extra blinding precaution, AMG 714 or placebo will be administered by qualified personnel not involved in the vitiligo assessment of the study participant.

## 3.5.2 Procedure for Unblinding / Unmasking

Before the study is complete, the blind for an individual participant should only be broken when appropriate medical management of the participant necessitates knowledge of treatment assignment.

In the event of a medical emergency, when the immediate knowledge of the actual treatment is essential for the management of the participant, the site PI, or designee, can automatically obtain the participant's treatment assignment from the randomization system. The site PI is encouraged to discuss the emergency unblinding with the NIAID Medical Monitor prior to unblinding the participant, if possible.

If the randomization system is not available, the site PI can contact the Clinical Data and Safety Management Center (CDSMC) Client Support Services to obtain treatment assignment information. For more information and other unblinding pathways, please refer to the study Manual of Procedures (MOP).

As soon as possible, the site investigator will provide a full account of unblinding to the NIAID Medical Monitor, Protocol Chair, and the Statistical and Clinical Coordinating Center (SCCC) of the unblinding event. The NIAID Medical Monitor will then notify the Data and Safety Monitoring Board (DSMB). A full account of the event will be recorded, including the date and time of the unblinding, the names of the individual(s) who made the decision, the

reason(s), the participant(s) affected, and individual(s) who were unblinded, and individual(s) who were notified.

Unblinding the treatment of an individual participant or subgroups of participants for unplanned interim analyses to support DSMB reviews and final analysis will require written approval from NIAID.

IND safety reports will be reported to the FDA, DSMB, and IRBs in an unblinded fashion.

The final study report will contain any instances of unblinding prior to completion of the study along with the reason(s) for unblinding.

### 4. SELECTION OF PARTICIPANTS

#### 4.1 RATIONALE FOR STUDY POPULATION

This study will recruit adults with vitiligo from age 18 to 75 years. Clinical diagnosis of vitiligo by a dermatologist is required to ensure vitiligo is correctly diagnosed. Vitiligo involvement of the face is required since facial repigmentation is the primary endpoint. Individuals with vitiligo that is segmental, or who have more than 33% leukotrichia on the face or total body will be excluded since these lesions are not expected to repigment. Some prior treatments for vitiligo within specific time periods will be excluded to avoid confounding of the results by prior therapy.

### 4.2 INCLUSION CRITERIA

Individuals must meet all of the following criteria to be eligible for enrollment as study participants:

- 1. Adults 18-75 years of age.
- 2. Clinical diagnosis of active or stable vitiligo made by a dermatologist, as defined in Section 3.4.2.
- 3.  $F\text{-VASI} \ge 0.25$  (Appendix 2).
- 4.  $T\text{-VASI} \ge 3$  (Appendix 2).
- 5. Willingness to:
  - a) Undergo nbUVB phototherapy, as outlined in Section 7.3.
  - b) Stop all other treatments for vitiligo from screening through the final follow up visit as outlined in Section 7.2.

#### 4.3 EXCLUSION CRITERIA

Individuals who meet any of the following criteria are not eligible for enrollment as study participants:

- 1. Inability or unwillingness of a participant to give written informed consent or comply with the study protocol.
- 2. Segmental vitiligo.
- 3. Contraindication to nbUVB phototherapy.

- 4. More than 33% leukotrichia on the face or on the total body.
- 5. Use of biologic immunosuppressive or immunomodulatory agents, or investigational therapy or procedure within 12 weeks or 5 half-lives prior to Visit 0 (whichever is longer), except agents authorized for prevention and treatment of SARS-CoV-2 infection according to FDA Emergency Use Authorization (EUA).
- 6. Use of laser or light-based treatment (phototherapy) including tanning beds within 8 weeks prior to Visit 0.
- 7. Use of non-biologic systemic or topical immunosuppressive or immunomodulatory agents within 4 weeks prior to Visit 0.
- 8. History of melanocyte-keratinocyte transplantation procedure (MKTP) or other surgical treatment for vitiligo.
- 9. Current or past use of the depigmenting agent monobenzyl ether of hydroquinone, including Benoquin® (Monobenzone).
- 10. Presence of skin conditions or lesions that would confound the vitiligo assessments.
- 11. Spontaneous repigmentation within 6 months prior to Visit 0 (repigmentation without any treatment and significant in amount as determined by the investigator).
- 12. Uncontrolled thyroid function at screening as determined by the investigator. If the participant has a history of thyroid disease and is on treatment, the participant must be on a stable thyroid regimen for at least three months prior to Visit 0.
- 13. Greater than 3 adequately treated nonmetastatic basal cell carcinomas (BCC) or squamous cell carcinomas (SCC) within 12 months prior to Visit 0; or previous history of multiple BCC or SCC which may pose additional risks from participation in the study in the opinion of the investigator.
- 14. Previous or current diagnosis of other cancer, except adequately treated cervical carcinoma in situ.
- 15. Acute or chronic infection, including current use of suppressive therapy for chronic infection, hospitalization for treatment of infection within 90 days prior to Visit 0, or parenteral anti-microbial (including anti-bacterial, anti-viral, or anti-fungal agents) use within 90 days prior to Visit 0.
- 16. Evidence of infection, including:
  - a) Human immunodeficiency virus (HIV)
  - b) Current or prior infection with hepatitis B (HBV), as indicated by positive HBsAg or positive HBcAb
  - c) Current or prior hepatitis C (HCV), unless treated with anti-viral therapy with achievement of a sustained virologic response (undetectable viral load 12 weeks after cessation of therapy)
  - d) Positive Quantiferon-TB Gold or Quantiferon-TB Gold Plus test. PPD or T-SPOT.TB test may be substituted for Quantiferon-TB Gold or Quantiferon-TB Gold Plus test
- 17. Any of the following laboratory abnormalities:
  - a) White blood count (WBC)  $< 3.5 \times 10^3/\mu L$

- b) Hemoglobin < 10 g/dL
- c) Platelets (Plt)  $< 125,000/\text{mm}^3$
- d) Alanine aminotransferase (ALT)  $\geq 2x$  ULN
- e) Aspartate aminotransferase (AST)  $\geq 2x$  ULN
- 18. Women of child-bearing potential who are unwilling to use a medically acceptable form of contraception or be sexually inactive by abstinence until study Week 48 (Section 7.4). Contraception or abstinence is required for 2 weeks prior to Visit 0.
- 19. Women who are pregnant or lactating.
- 20. Vaccination with a live attenuated vaccine within 30 days prior to Visit 0.
- 21. Known drug allergy or reaction to any component of AMG 714 (Section 6.1.1) or proteins derived from mammalian cell lines.
- 22. Past or current medical problems or findings from physical examination or laboratory testing, which, in the opinion of the investigator, may pose additional risks from participation in the study, may interfere with the participant's ability to comply with study requirements or that may impact the quality or interpretation of the data obtained from the study.
- 23. Current, diagnosed mental illness (e.g. severe depression) or current, diagnosed or self-reported drug or alcohol abuse that, in the opinion of the investigator, would interfere with the participant's ability to comply with study requirements.

